2.0 STUDY OBJECTIVES

The objective of this study is to compare the safety and efficacy of two different concentrations of ST-100 Ophthalmic Solution to placebo for the treatment of the signs and symptoms of dry eye.

3.0 CLINICAL HYPOTHESIS

The clinical hypotheses for this study is that low dose and high dose ST-100 Ophthalmic Solution twice daily (BID) is superior to its vehicle (BID) for the primary endpoints of signs and symptoms of dry eye, as follows:

- Sign: Pre-Controlled Adverse Environment (CAE®) total corneal fluorescein staining score on the Ora Calibra® scale, measured by [REDACTED]
[REDACTED]
- Symptom: Pre-CAE® ocular discomfort scale on the Ora Calibra® Ocular Discomfort scale, measured by [REDACTED]

4.0 OVERALL STUDY DESIGN

This is a Phase 2, multi-center, double-masked, randomized, placebo-controlled clinical study. Subjects will be randomized to one of the following treatment arms at Visit 2 (Day 1):

- Low dose ST-100 Ophthalmic Solution: [REDACTED]
- High dose ST-100 Ophthalmic Solution: [REDACTED]
- Placebo Ophthalmic Solution (Vehicle): [REDACTED]

Approximately 150 subjects will be randomly assigned to one of the three groups (1:1:1) to receive either ST-100 Ophthalmic Solution or placebo solution as topical ophthalmic drops administered bilaterally BID for 4 weeks. Subjects, Sponsor, Contract Research Organization (CRO), and site personnel will be masked to treatment assignment.

[figure not shown]
During the 7-day study run-in period prior to randomization, all subjects will receive Placebo Ophthalmic Solution (Vehicle) bilaterally BID.

[figure not shown]
During the screening period, two 90-minute exposures to the CAE® will be conducted to ascertain eligibility to enter the study at Visit 1 (Day -7 ± 1) and Visit 2 (Day 1). Subjects who qualify after the initial screening visit will enter the run-in phase, where they will self-administer vehicle BID for approximately 7 days. Those who qualify at Visit 2 (Day 1) will be randomized to receive study drug in a double-masked fashion for 28 days. Subjects will self-administer drops BID and will complete daily diary assessments as instructed.

The CAE® exposure will occur at Visit 1 (Day -7 ± 1), Visit 2 (Day 1), Visit 5 (Day 8 ± 1), Visit 6 (Day 15 ± 1), and Visit 7 (Day 29 ± 2), with Pre-CAE®, during CAE® and Post-CAE® assessments of ocular signs and symptoms.

At Visit 3 (Day 2 ± 2 h) and Visit 4 (Day 4 ± 2 h), no CAE® exposure will occur but signs and symptoms will be assessed for 24h recovery post-CAE® and 72h recovery post-CAE®. Study drug will be discontinued at Visit 7. Subjects will exit from the study at this visit.

The total number of expected participants, including screen failures, is approximately 300 subjects. A study design flow chart is provided below:

5.0 STUDY POPULATION

5.1 NUMBER OF SUBJECTS (APPROXIMATE)

It is estimated that approximately █ subjects will be screened to enroll approximately █ randomized subjects (█ in each group). Subjects will be randomized in each treatment arm. Subjects will be randomized in a 1:1:1 ratio of

- High dose ST-100 Ophthalmic Solution
- Low dose ST-100 Ophthalmic Solution
- Placebo Ophthalmic Solution (Vehicle)

5.2 STUDY POPULATION CHARACTERISTICS

All subjects must be at least 18 years of age, of either gender, and of any race, and must meet all inclusion criteria and none of the exclusion criteria.

5.3 INCLUSION CRITERIA

Each subject must:

1. Be at least 18 years of age;
2. Provide written informed consent;
3. Have a reported history of dry eye for at least 6 months prior to Visit 1;
4. Have a history of use or desire to use eye drops for dry eye symptoms within 6 months of Visit 1, except as noted below in [Section 5.4\(6\)](#);
5. Report a score of [REDACTED] on the Ora Calibra® Ocular Discomfort & 4-symptom questionnaire in at least one symptom pre-CAE® at Visits 1 and 2;
6. Have a Schirmer's Test score of [REDACTED] at Visits 1 and 2;
7. Have a conjunctival redness score [REDACTED] according to the Ora Calibra® Conjunctival Redness for Dry Eye Scale in at least one eye pre-CAE® at Visits 1 and 2;
8. Have a corneal fluorescein staining score of [REDACTED] in at least one region (e.g. inferior, superior, or central) pre-CAE® at Visits 1 and 2;
9. Have a sum corneal fluorescein staining score of [REDACTED] based on the sum of the inferior, superior, and central regions, pre-CAE® at Visits 1 and 2;
10. Have a total lissamine green conjunctival score of [REDACTED] based on the sum of the temporal and nasal regions pre-CAE® at Visits 1 and 2;
11. Demonstrate a response to the CAE® at Visits 1 and 2 as defined by:
 - a) Having at least a [REDACTED] point increase in fluorescein staining in the inferior region in at least one eye following CAE® exposure
 - b) Reporting an Ora Calibra® Ocular Discomfort Score [REDACTED] at 2 or more consecutive time points in at least one eye during CAE® exposure
[REDACTED]
[REDACTED]
12. Have at least one single eye satisfy all criteria for 6, 7, 8, 9, 10 and 11 above.

5.4 EXCLUSION CRITERIA

Each subject may not:

1. Have any clinically significant slit lamp findings at Visit 1 that may include active blepharitis, meibomian gland dysfunction, lid margin inflammation, or active ocular allergies that require therapeutic treatment, and/or in the opinion of the investigator may interfere with study parameters;
2. Be diagnosed with an ongoing ocular infection (bacterial, viral, or fungal), or active ocular inflammation at Visit 1;
3. Have worn contact lenses within 7 days of Visit 1 or anticipate using contact lenses during the study;

4. Have used any eye drops within 2 hours of Visit 1;
5. Have previously had laser-assisted in situ keratomileusis (LASIK) surgery within the last 12 months;
6. Have used Restasis, Xiidra, or Cequa ophthalmic solutions within 45 days of Visit 1;
7. Have any planned ocular and/or lid surgeries over the study period or any ocular surgery within the last 6 months;
8. Have used, are using or anticipate using permanent or temporary punctal plugs during the study within 30 days of Visit 1;
9. Be currently taking any topical ophthalmic prescription (including medications for glaucoma) or over-the-counter solutions, artificial tears, gels or scrubs, or using a moisture chamber and cannot discontinue these medications for the duration of the trial (excluding medications allowed for the conduct of the study);
10. Be currently taking or have taken Omega-3 supplements within the last 3 months;
11. Have corrected visual acuity (VA) greater than or equal to Logarithm of the Minimum Angle of Resolution (logMAR) █ as assessed by Early Treatment of Diabetic Retinopathy Study (ETDRS) scale in both eyes at Visit 1;
12. Be a woman who is pregnant, nursing, or planning a pregnancy;
13. Be unwilling to submit a urine pregnancy test at Visit 1 and Visit 5 (or early termination visit) if of childbearing potential. Non-childbearing potential is defined as a woman who is permanently sterilized (e.g. has had a hysterectomy or tubal ligation), or is post-menopausal (without menses for 12 consecutive months);
14. Be a woman of childbearing potential who is not using an acceptable means of birth control; acceptable methods of contraception include: hormonal – oral, implantable, injectable, or transdermal contraceptives; mechanical – spermicide in conjunction with a barrier such as a diaphragm or condom; intrauterine device; or surgical sterilization of partner. For non-sexually active females, abstinence may be regarded as an adequate method of birth control; however, if the subject becomes sexually active during the study, she must agree to use adequate birth control as defined above for the remainder of the study;
15. Have a known allergy and/or sensitivity to the test article or its components;
16. Have a condition or be in a situation that the investigator feels may put the subject at significant risk, may confound the study results, or may interfere significantly with the subject's participation in the study;
17. Be currently enrolled in an investigational drug or device study or have used an investigational drug or device within 30 days of Visit 1;
18. Be currently using any medication known to cause ocular drying that is not used on a stable dosing regimen for at least 30 days prior to Visit 1;
19. Have a known history of meibomian gland procedures (e.g., LipiFlow, LPI, probing, etc.) within 6 months of study enrollment;
20. Be unable or unwilling to follow instructions, including participation in all study assessments and visits.

5.5 WITHDRAWAL CRITERIA (IF APPLICABLE)

If at any time during the study the investigator determines that a subject's safety has been compromised, the subject may be withdrawn from the study.

Subjects may withdraw consent from the study at any time.

Sponsor and/or investigator may discontinue any subject for non-compliance or any valid medical reason (see [Section 8.6.2](#)).

If a subject discontinues participation in the study early, every attempt will be made to complete the exit procedures required at the final study visit (Visit 7).

6.0 STUDY PARAMETERS

6.1 EFFICACY ENDPOINTS

6.1.1 Primary Efficacy Endpoints

The primary efficacy endpoint (sign) is:

- Total corneal fluorescein staining score on the Ora Calibra® scale, measured by [REDACTED]

The primary efficacy endpoint (symptom) is:

- Ocular discomfort score on the Ora Calibra® Ocular Discomfort Scale, measured by [REDACTED]

6.1.2 Secondary Efficacy Endpoints

The secondary efficacy endpoints are:

- Fluorescein staining (Ora Calibra® scale) at Visits 3, 4, 5, 6, and 7 (pre-CAE®, post-CAE®, and pre- to post-CAE®): regions: [REDACTED]
- Lissamine green staining (Ora Calibra® scale) at Visits 3, 4, 5, 6, and 7 (pre-CAE®, post-CAE®, and pre- to post-CAE®): regions: [REDACTED]
- Tear film break-up time (TFBUT) at Visits 3, 4, 5, 6, and 7 (pre-CAE®, post-CAE®, and pre- to post-CAE®)
- Conjunctival Redness at Visits 3, 4, 5, 6, and 7 (pre-CAE®, post-CAE®, and pre- to post-CAE®)
- Drop comfort assessment after randomization at Visit 2
- Ocular Surface Disease Index (OSDI) at Visits 3, 4, 5, 6, and 7 (pre-CAE®)
- Ocular discomfort Scale during CAE® at Visits 4, 5, 6, and 7
- Daily diary
- Visual Analog Scale – Burning/Stinging, Itching, Foreign Body Sensation, Blurred Vision, Eye Dryness, Photophobia, Pain at Visits 3, 4, 5, 6, and 7 (pre-CAE®)
- Unanesthetized Schirmer's Test at Visit 7 (pre-CAE®)

- Ocular Discomfort Scale outside of the CAE® at Visits 3, 4, 5, 6, and 7 (pre-CAE®, post-CAE®, and pre- to post-CAE®)
- Four symptom questionnaire at Visits 3, 4, 5, 6, and 7 (pre-CAE®, post-CAE®, and pre- to post-CAE®)

6.2 SAFETY MEASURES

The safety measures being evaluated are:

- Visual acuity
- Slit-lamp evaluation
- Adverse event query
- Intraocular pressure
- Undilated fundoscopy

7.0 STUDY MATERIALS

7.1 STUDY TREATMENTS

7.1.1 Study Drug Formulation

All arms will be double-masked. Subjects will be randomized 1:1:1 into:

- High dose ST-100; BID
- Low dose ST-100; BID
- Placebo Ophthalmic Solution (Vehicle); BID

ST-100 Ophthalmic Solution will be formulated as a sterile solution at [REDACTED] for topical ophthalmic administration and is intended for clinical use. The study drug will be supplied in blow-fill seal ampoules, which allow for product administration directly to the eye. Each ampoule will contain a nominal volume of 0.25 mL.

The excipients which will be used to manufacture ST-100 Ophthalmic Solution will be standard excipients for use in ophthalmic solutions that comply with their respective USP / EP monographs.

The placebo for ST-100 Ophthalmic Solution contains all the same excipients used in the active formulation without the peptide.

7.1.2 Description of and Justification for the Route of Administration, Dosage, Dosage Regimen, and Treatment Period.

Topical ophthalmic dosing is the optimal route of administration for dry eye treatments. The dosage and dosage regimen were selected based on positive efficacy results in the proof-of-concept nonclinical studies. The proposed treatment period is 4 weeks.

7.1.3 Instructions for Use and Administration

- Subjects will receive placebo ophthalmic solution at Visit 1, and assigned study drug kit at Visit 2, 5 and 6.
- Subjects who are randomized must administer study drug in each eye BID. At Visit 2 and 6, subjects will self-administer one dose of study drug in office. Subjects should NOT self-administer study drug at home on the morning of their scheduled Visit 2 and Visit 6.

7.2 LABELING, PACKAGING, STORAGE, ACCOUNTABILITY, AND RETURN OR DISPOSAL OF INVESTIGATIONAL PRODUCT

7.2.1 Labeling/Packaging

Investigational product (IP) will be packaged and labeled into clinical kits. The primary packaging of the ST-100 will be blow-fill-seal ampules with a fill volume of [REDACTED]. The secondary packaging is a foil pouch that contains three ampules in each pouch. Each clinical kit will contain 6 pouches, for a total of 18 ampules per kit.

Run-in Period

For the run-in period, each subject will receive 1 kit.

Treatment Period

BID Dosing: For the treatment period, each subject will receive 1 kit at Visit 2, 1 kit at Visit 5 and 2 kits at Visit 6.

7.2.2 Storage of Investigational Product

Ampoules must be stored at 2 to 8°C until the time of use. The ampoules are to be kept refrigerated at the study site and by the subject at their home. Any material remaining in the ampoule after use should be discarded. ST-100 Ophthalmic Solution should be kept out of reach of children. Drug administration instructions and discarding information will be provided with each study.

7.2.3 Accountability of Investigational Product

The IP is to only be prescribed by the Principal Investigator (PI) or his/her named sub-investigator(s), and is to only be used in accordance with this protocol. The IP must only be distributed to subjects properly qualified under this protocol to receive IP.

The Investigator must keep an accurate accounting of the IP received from the supplier. This includes the amount of IP dispensed to subjects, amount of IP returned to the investigator by the subjects, and the amount returned or disposed upon the completion of the study. A detailed inventory must be completed for the IP.

7.2.4 Return or Disposal of Investigational Product

All IP (used or unused) will be returned to the sponsor or their designee. The return of IP will be specified in writing.

7.3 OTHER STUDY SUPPLIES

Other study supplies include Schirmer's test strips, sodium fluorescein, lissamine green, Fluress, Tropicamide, and daily diary.

8.0 STUDY METHODS AND PROCEDURES

8.1 SUBJECT ENTRY PROCEDURES

8.1.1 Overview

Subjects as defined by the criteria in [Section 5.3](#) and [Section 5.4](#) will be considered for entry into this study.

8.1.2 Informed Consent

Prior to a subject's participation in the study (i.e., changes in a subject's medical treatment and/or study related procedures), the study will be discussed with each subject, and subjects wishing to participate must give written informed consent using an informed consent form. The informed consent form must be the most recent version that has received approval/favorable review by a properly constituted Institutional Review Board (IRB).

8.1.3 Washout Intervals

Prohibited medications, treatments, and activities are outlined in the exclusion criteria ([Section 5.4](#))

8.1.4 Procedures for Final Study Entry

Subjects must meet all inclusion and none of the exclusion criteria ([Section 5.3](#) and [5.4](#)).

8.1.5 Methods for Assignment to Treatment Groups:

Before the initiation of study run-in at Visit 1, each subject who provides written informed consent will be assigned a screening number. All screening numbers will be assigned in strict numerical sequence at a site and no numbers will be skipped or omitted. Each subject who meets all the inclusion and none of the exclusion criteria at Visit 1 and Visit 2 will be assigned a randomization number at the end of Visit 2. The Interactive Web Response System (IWRS) will be used to assign all randomization numbers.

Randomization and kit numbers will be assigned automatically to each subject as they are entered into the IWRS.

The site staff will dispense kit(s) required until the next visit. Both the randomization number and the dispensed study drug kit number(s) will be recorded on the subject's source document and electronic case report form (eCRF). Subjects, Sponsor, CRO, and site personnel will be masked to treatment assignment.

8.2 CONCURRENT THERAPIES

The use of any concurrent medication, prescription or over the counter, is to be recorded on the subject's source document and corresponding eCRF along with the reason the medication was taken.

Concurrent enrollment in another investigational drug or medical device study is not permitted.

8.2.1 Prohibited Medications/Treatments

Disallowed medications/treatments during the study are outlined in the Exclusion Criteria ([Section 5.4](#)).

8.2.2 Escape Medications

No escape medications are required for this study.

8.2.3 Special Diet or Activities

No special diets or activities are required for this study.

8.3 EXAMINATION PROCEDURES

An Informed Consent Form (ICF) must be signed and dated by the subject, the PI or designee and witness (if required) before any study-related procedures are performed.

8.3.1 Procedures to be Performed at Each Study Visit with Regard to Study Objectives

Procedures listed below should be performed in the given order. See [Appendix 1](#) for the Schedule of Visits and Measurements [Appendix 2](#) for details on methodologies and grading systems.

8.3.2 Visit 1: Day -7 ± 1 – CAE® Screening

All subjects will undergo the following screening assessments:

Pre-CAE®

- Informed Consent/Health Insurance Portability and Accountability Act (HIPAA)
- Demographic Data and Medical/Medication/Ocular History
- Review of Inclusion/Exclusion Criteria
- Urine Pregnancy Test (for females of childbearing potential): Women of childbearing potential must have a negative urine pregnancy test to continue in the study
- Ora Calibra® Ocular Discomfort Scale
- Ora Calibra® Ocular Discomfort & 4-Symptom Questionnaire
- OSDI Questionnaire
- Visual Analog Scale (VAS) Symptom Assessment
- Visual Acuity (ETDRS)
- Conjunctival Redness
- Slit Lamp Biomicroscopy
- TFBUT
- Fluorescein Staining
- Lissamine Green Staining
- At least 15-minute wait between lissamine green staining and Schirmer's test
- Schirmer's test
- At least 15 minute wait between Schirmer's test and CAE® exposure
- Adverse Event (AE) Query

- 90-minute CAE® exposure

Post-CAE®

- Ora Calibra® Ocular Discomfort Scale
- Ora Calibra® Ocular Discomfort & 4-Symptom Questionnaire
- Conjunctival Redness
- Slit Lamp Biomicroscopy
- TFBUT
- Fluorescein Staining
- Lissamine Green Staining
- Intraocular Pressure (IOP)
- Undilated Fundoscopy
- Review of Inclusion/Exclusion Criteria
- Run-in (Vehicle) and Diary Dispensation: Prior to discharge from the study site on Visit 1, subjects will be dispensed sufficient Run-in supply to last until Visit 2 and will be educated in diary recording and self-administration of vehicle run-in. Subjects will be instructed to self-administer one drop BID in each eye until Visit 2. Subjects will be instructed NOT to instill run-in on the morning of their next scheduled study visit (Visit 2).
- AE Query
- Subjects will be scheduled for Visit 2.

8.3.3 Visit 2: Day 1 – CAE® Confirmation and Baseline

Pre-CAE®

- Study Diary/Run-in Collection
- Confirm subject has NOT administered their morning study drug dose at home
- Medical and Medication History Update
- Review of Inclusion/Exclusion Criteria
- AE query
- Ora Calibra® Ocular Discomfort Scale
- Ora Calibra® Ocular Discomfort & 4-Symptom Questionnaire
- OSDI Questionnaire
- VAS Symptom Assessment
- Visual Acuity (ETDRS)
- Conjunctival Redness

- Slit Lamp Biomicroscopy
- TFBUT
- Fluorescein Staining
- Lissamine Green Staining
- At least 15-minute wait between lissamine green staining and Schirmer's test
- Schirmer's test
- AE Query
- At least 15 minute wait between Schirmer's test and CAE® exposure
- 90-minute CAE® exposure;

Post-CAE®

- Ora Calibra® Ocular Discomfort Scale
- Ora Calibra® Ocular Discomfort & 4-Symptom Questionnaire
- Slit Lamp Biomicroscopy
- Conjunctival Redness
- TFBUT
- Fluorescein Staining
- Lissamine Green Staining
- Review of Inclusion/Exclusion Criteria
- Randomization
- Study Drug Diary/Study Drug Dispensation: Prior to discharge from the study site on Visit 2 (Day 1), randomized subjects will be educated in study drug diary recording and self-administration of study drug. Subjects will receive their assigned study drug kit with sufficient supply to last until Visit 3
- Study Drug Instillation at the Study Site: All subjects having a positive response and meeting all other screening eligibility criteria at the end of Visit 2 will be randomized to one of the three treatment groups utilizing the IWRS system. Randomized subjects will self-administer their initial study drug dose bilaterally at the study site under supervision of a trained technician
- Ora Calibra® Drop Comfort Scale
- AE Query
- Subjects will be scheduled for Visit 3

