9.0 ADVERSE EVENTS

9.1 ADVERSE EVENT (AE)

An AE is defined as any untoward medical occurrence associated with the use of an IP in humans, whether or not considered IP-related. An AE can be any unfavorable and unintended sign (e.g., an abnormal laboratory finding), symptom, or disease temporally associated with the use of an IP, without any judgment about causality. An AE can arise from any use of the IP (e.g., off-label use, use in combination with another drug or medical device) and from any route of administration, formulation, or dose, including an overdose. An AE can arise from any delivery, implantation, or use of a medical device, including medical device failure, subject characteristics that may impact medical device performance (e.g., anatomical limitations), and therapeutic parameters (e.g., energy applied, sizing, dose release, and anatomic fit) associated with medical device use.

All AEs spontaneously reported by the subject and/or in response to an open question from study personnel or revealed by observation, physical examination or other diagnostic procedures will be recorded in the source document and on the appropriate pages of the case report form (CRF). Any clinically relevant deterioration in clinical finding is considered an AE and must be recorded. When possible, signs and symptoms indicating a common underlying pathology should be noted as one comprehensive event.

Documentation regarding the AE should be made as to the nature, date of onset, end date, severity, and relationship to IP, action(s) taken, seriousness, and outcome of any sign or symptom observed by the physician or reported by the subject upon indirect questioning. Exacerbation of conditions related to the signs and symptoms of DED will not be reported as an AE.

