### 9.2 Missing or Inconclusive Data Handling

Imputation of missing data will be executed for partial or missing dates where complete dates are required to flag data as treatment-emergent or concomitant with treatment. Partial/missing start and end dates for AEs and concomitant medications will be imputed as follows:

Partial/missing start date:

25OCT2021

Confidential & Proprietary

Page 14 of 15

- Dates with missing day only will be imputed as the 1st of the month unless the month and year are same as the month and year of first dose of study medication, in which case missing day will be imputed as the first dose day of study medication.
- Dates with both day and month missing will be imputed as 1 Jan unless the year is same as the year of first dose of study medication, in which case missing day and month will be imputed as the first dose day and month of study medication.
- Completely missing dates will be imputed as the first dose date of study medication unless the end date is on or before the first dose date of study medication, in which case missing date will be imputed as 1 Jan of the same year as the end date.

Partial/missing end date:

- Dates with missing day only will be imputed as the last day of the month unless the month and year are the same as the month and year of the last dose of study medication, in which case missing day will be imputed as the last dose day of study medication.
- Dates with both day and month missing will be imputed as 31 Dec unless the year is same as the year of the last dose of study medication, in which case missing day and month will be imputed as the last dose day and month of study medication.
- If the ongoing flag is missing or “Yes” then the date will not be imputed unless death date is available, in which case the missing date will be imputed as the death date. If ongoing is “No” then the missing end date will be imputed as the last dose date.
- If the imputed date is after the date of death, then the end date will be set equal to the date of death.

The original dates will be displayed in data listings and the imputed dates will be used in derivations only (study day, treatment-emergence status, etc).

Missing data for the primary efficacy endpoints will be imputed using multiple imputation on the ITT population as specified in Estimand 1 for primary analyses.

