### 16.1 Adverse Events

An AE is defined as any untoward medical occurrence associated with the use of an IP in humans, whether or not considered IP-related. An AE can be any unfavorable and unintended sign (e.g., an abnormal laboratory finding), symptom, or disease temporally associated with the use of an IP, without any judgment about causality. An AE can arise from any use of the IP (e.g., off-label use, use in combination with another drug or medical device) and from any route of administration, formulation, or dose, including an overdose. An AE can arise from any delivery, implantation, or use of a medical device, including medical device failure, subject characteristics that may impact medical device performance (e.g., anatomical limitations), and therapeutic parameters (e.g., energy applied, sizing, dose release, and anatomic fit) associated with medical device use. All AEs will be coded using the MedDRA 24.0.

Treatment-emergent adverse events (TEAE) are defined as any event that occurs or worsens on or after the first dose of randomized study drug..

Severity of an AE is defined as a qualitative assessment of the degree of intensity of an AE as determined by the Investigator or reported to him/her by the subject. The assessment of severity is made irrespective of relationship to study drug or seriousness of the event and should be evaluated according to the following scale:

- *Mild*: Event is noticeable to the subject, but is easily tolerated and does not interfere with the subject's daily activities.
- *Moderate*: Event is bothersome, possibly requiring additional therapy, and may interfere with the subject's daily activities.
- *Severe*: Event is intolerable, necessitates additional therapy or alteration of therapy, and interferes with the subject's daily activities.

The relationship of each AE to the IP should be determined by the investigator using these explanations:

- *Definitely Related*: Relationship exists when the AE follows a reasonable sequence from the time of IP administration, follows a known response pattern of the drug class, is confirmed by improvement on stopping the IP and no other reasonable cause exists.
- *Probably Related*: Relationship exists when the AE follows a reasonable sequence from the time of IP administration, follows a known response pattern of the drug class, is confirmed by improvement on stopping the IP and the suspect IP is the most likely of all causes.

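### At Visit 2 the written AE queries and date-based rules cannot reliably separate events that begin before the first randomised dose from those that begin after it, so some pre-dose Day 1 events may be counted as TEAEs.

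*Protocol*

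**What the plan says.** **Order of procedures.** Protocol 8.3.1 states: "Procedures listed below should be performed in the given order". At Visit 2 (Protocol 8.3.3) an AE query stands near the start of the pre-CAE list and another after Schirmer's test, just before this step: "At least 15 minute wait between Schirmer's test and CAE® exposure". Next come the 90-minute CAE, two symptom instruments, slit lamp, redness, TFBUT, both stains, the eligibility review, randomisation and dispensation. Then: "Randomized subjects will self-administer their initial study drug dose bilaterally at the study site under supervision of a trained technician". The Drop Comfort Scale follows, and only then an AE query.

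**Data items.** Protocol 9.1: "Documentation regarding the AE should be made as to the nature, date of onset, end date, severity, and relationship to IP". Time of onset is not in the list. The same section excludes exacerbations of DED signs and symptoms from AE reporting. Under Protocol 9.3, AEs are collected from consent, so pre-dose Day 1 events are in scope as AEs.

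**Classification.** SAP 16.1 says TEAEs are "defined as any event that occurs or worsens on or after the first dose of randomized study drug". SAP 9.2 has missing dates imputed where "complete dates are required to flag data as treatment-emergent or concomitant with treatment", and uses the imputed dates to derive treatment-emergence status. No rule is visible for an event whose recorded onset date is the first-dose date. TEAEs judged possibly, probably or definitely related go into the treatment-related summaries (SAP 16.1).

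**The concern.** The first randomised dose is the boundary that defines treatment emergence, and at Visit 2 it falls partway through a long visit. Subjects have two dyes, Schirmer strips and a 90-minute provocation, then the dyes again, all on the same calendar date as the first dose. The one AE query that follows covers both the CAE period and the reaction to the first drop. If onset is held as a date, a pre-dose event and a post-dose event on Day 1 look alike in the data.

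What is at stake is how well the safety tables can be read. Procedure reactions that precede study drug could be added to the TEAE counts. Some could also be added to the treatment-related counts, because they are reported just after the first drop.

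**Working it through.** The plan states no figure on this point, so there is nothing to reproduce. The check has two parts: a reading of the rules, and an illustration of size under stated assumptions.

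**1. Is there a query between the CAE and the dose?** None is listed at Visit 2. Visits 5 and 7 (Protocol 8.3.6, 8.3.8) do list one after the post-CAE tests with no dose in between. Visit 6 (8.3.7) has the same order as Visit 2, but there every event is already after the first dose, so no boundary is at risk.

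**2. Would the recorded data settle the order?** Protocol 9.1 asks for onset date. SAP 9.2 works with dates. SAP section 10 keeps date and time for randomisation, but no text mentions a time for AE onset. Even an event picked up by one of the two pre-CAE queries carries the first-dose date. An extra query alone would therefore not be enough.

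**3. Which way would a Day 1 date be read?** The plan does not say. SAP 9.2 moves a start date with a missing day, in the month of first dose, to the first-dose day. That is a cautious rule only if onset on the first-dose date counts as treatment-emergent. The default is thus a reasonable inference, not a stated rule.

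**4. Would the tables reveal it?** The onset-day summary in SAP 16.1 has Day 8 or earlier as its first band, so a cluster on Day 1 would not show.

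**5. Size, for illustration.** Let p be the true TEAE proportion in an arm and b the proportion of subjects with a reportable pre-dose Day 1 event. Assume that b is independent of p, that b is the same in each arm because these events precede randomisation, and that every such event is misclassified. Then:

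- shown rate = 1 − (1 − p)(1 − b)
- shown difference = (1 − b) × true difference

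The 50 subjects per arm come from the Protocol synopsis. The true rates of 10% and 4% and the values of b are assumptions.

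| b | Subjects per arm with such an event (50b) | Shown rates | Difference (points) | Ratio |
|---|---|---|---|---|
| 0 | 0 | 10.0% v 4.0% | 6.0 | 2.50 |
| 2% | 1 | 11.8% v 5.9% | 5.9 | 1.99 |
| 5% | 2.5 | 14.5% v 8.8% | 5.7 | 1.65 |
| 10% | 5 | 19.0% v 13.6% | 5.4 | 1.40 |

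Example at b = 5%: 1 − 0.90 × 0.95 = 0.145; 1 − 0.96 × 0.95 = 0.088; 0.145 − 0.088 = 0.057; 0.145 / 0.088 = 1.65.

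A second pair of assumed true rates, 20% v 10%, gives the same picture. At b = 1%, 5% and 10% the difference goes from 10.0 to 9.9, 9.5 and 9.0 points, and the ratio from 2.00 to 1.91, 1.66 and 1.47. With equal true rates of 10%, both arms show 14.5% at b = 5%, so no difference is created.

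**The case against.** A reader might infer that pre-dose Day 1 events *are* counted as TEAEs. The documents do not say so. SAP 16.1 and the Protocol synopsis tie treatment emergence to the dose, not to the calendar day, so an event known to precede the first randomised dose is not a TEAE under those texts. The SAP 9.2 sentence on dates concerns partial or missing dates and does not classify fully dated Day 1 events. This stands: the most that can be said is that such events may be counted.

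A reader might also infer that onset is recorded by date only. That rests on the list in Protocol 9.1. The AE eCRF is not available and the visit schedules in both appendices are not shown, so a time field or a further query may exist.

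Other points for the plan also stand:

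- Capture does not depend on scheduled queries. Sites record "All AEs spontaneously reported by the subject and/or in response to an open question from study personnel or revealed by observation" or examination, and several examinations fall between the CAE and the dose. This helps detection but does not supply an onset time.
- Excluding DED exacerbations removes much of what a dry-eye provocation would produce. Mainly dye, strip and other non-DED reactions remain.
- Protocol 9.1.2 tells the investigator to weigh the timing of the event relative to drug, which limits wrong attribution.
- Visits 5, 6 and 7 also include the dyes and a CAE. Reactions there are TEAEs in every arm by definition, so some procedural background remains whatever is done at Visit 2. Nothing shows that Day 1 is the worst day.
- A hidden difference in first-dose tolerability is not supported. The risk difference hardly moves, no ratio or test of TEAEs is visible in the plan, and the Drop Comfort Scale measures tolerability directly after the first dose.
- Counting an ambiguous same-day event as a TEAE is a recognised cautious convention. But the plan does not state it as a rule, and a better record would leave fewer events ambiguous.

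**Conclusion.** The point holds as a gap in separability. As written, the Visit 2 order, the AE data items and the date-based derivation cannot reliably tell pre-dose from post-dose Day 1 events, so non-DED events that precede the first randomised dose may be reported as TEAEs.

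The likely consequence is modest. Absolute TEAE and treatment-related rates may be somewhat too high, and ratios diluted. Under the assumed 2% to 10% background, a true 6.0-point difference would show as 5.9 to 5.4 points and a ratio of 2.5 as 1.99 to 1.40. These figures are an upper bound for each b, because they take every such event as misclassified. The effect is expected to be equal across arms, creates no expected difference between them, and does not touch the primary endpoints. The true b is not in the documents. The conclusion would fall away if the eCRF already captures time of onset and the programming uses it. The change is worth making because it is cheap, not because the bias is large.

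**What to change.** 1. **Protocol 8.3.3:** add an AE query after the post-CAE assessments and before randomisation and instillation.
2. **AE eCRF:** for events dated Day 1, record whether onset was before or after the first randomised dose, unless onset time is already captured.
3. **SAP 16.1:** classify Day 1 events by that field. Count an event as a TEAE if the field is missing, or if it began before the dose and worsened after it.

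The cost is one extra question at Visit 2, one extra eCRF field and one SAP sentence.
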